#### Non-measurable disease.

All other lesions are considered non-measurable, including small lesions (longest diameter < 10mm or pathological lymph nodes with ≥ 10 to < 15 mm short axis) as well as truly non-measurable lesions. Lesions considered truly non-measurable include: leptomeningeal disease, ascites, pleural or pericardial effusion, inflammatory breast disease, lymphangitic involvement of skin or lung, abdominal masses/abdominal organomegaly identified by physical exam that is not measurable by reproducible imaging techniques.

#### Target lesions.

All measurable lesions up to a maximum of five lesions total (and a maximum of two lesions per organ) representative of all involved organs should be identified as target lesions

Non-target lesions. All other lesions (or sites of disease) including any measurable lesions over and above the five target lesions should be identified as **non-target lesions** and should also be recorded at baseline. Measurements of these lesions are not required, but the presence or absence of each should be noted throughout follow-up.

#### 6.1.3 Methods for Evaluation of Measurable Disease

All measurements should be taken and recorded in metric notation using a ruler or calipers. All baseline evaluations should be performed as closely as possible to the beginning of treatment and not more than 60 days before the beginning of the treatment.

Conventional CT should be performed with cuts of 10 mm or less in slice thickness contiguously. Spiral CT should be performed using a 5 mm contiguous reconstruction algorithm.

The cytological confirmation of the neoplastic origin of any effusion that appears or worsens during treatment when the measurable tumor has met criteria for response or stable disease is mandatory to differentiate between response or stable disease (an effusion may be a side effect of the treatment) and progressive disease.

#### 6.1.4 Response Criteria

#### 6.1.4.1 Evaluation of Target Lesions

Complete Response (CR): Disappearance of all target lesions. Disappearance of all target lesions. Any pathological lymph nodes (whether target or non-target) must have reduction in short axis to <10 mm (the sum may not be "0" if there are target nodes). Determined by two separate observations conducted not less than 4 weeks apart. There can be no appearance of new lesions.

Partial Response (PR): At least a 30% decrease in the sum of the longest diameter (LD) of target lesions, taking as reference the baseline sum LD. There can be no appearance of new lesions.

Progressive Disease (PD): > 20% increase in the SLD taking as reference the smallest SLD recorded since the treatment started (nadir) and minimum 5 mm increase over the nadir.

Stable Disease (SD): Neither sufficient shrinkage to qualify for PR nor sufficient increase to qualify for PD, taking as reference the smallest sum LD since the treatment started. There can be no unequivocal new lesions.

#### 6.1.4.2 Evaluation of Non-Target Lesions

Complete Response (CR): Disappearance of all non-target lesions and normalization of tumor marker level. All lymph nodes must be non-pathological in size (< 10 mm short axis).

Incomplete Response/Stable Disease (Non-CR/Non-PD): Persistence of one or more non-target lesion(s) and/or maintenance of tumor marker level above the normal limits.

Progressive Disease (PD): Appearance of one or more new lesions and/or unequivocal progression of existing non-target lesions

## 6.1.4.3 Evaluation of Best Overall Response

The best overall response is the best response recorded from the start of the treatment until disease progression/recurrence (taking as reference for progressive disease the smallest measurements recorded since the

treatment started). The subject's best response assignment will depend on the achievement of both measurement and confirmation criteria.

Time point response: patients with target (+/– non-target) disease.			
		New	Overall
Target lesions	Non-target lesions	lesions	response
CR	CR	No	CR
CR	Non-CR/non-PD	No	PR
CR	Not evaluated	No	PR
PR	Non-PD or not all evaluated	No	PR
SD	Non-PD or not all evaluated	No	SD
Not all evaluated	Non-PD	No	NE
PD	Any	Yes or No	PD
Any	PD	Yes or No	PD
Any	Any	Yes	PD

CR = complete response, NE = not evaluable, PD = progressive disease, PR = partial response, SD = stable disease.

Time point response: patients with non-target disease only.			
Non-target lesions	New lesions	Overall response	
CR	No	CR	
Non-CR/non-PD	No	Non-CR/non-PD	
Not all evaluated	No	NE	
Unequivocal PD	Yes or No	PD	
Any	Yes	PD	

CR = complete response, NE = not evaluable, PD = progressive disease

A 'Non-CR/non-PD' is preferred over 'stable disease' for non-target disease since SD is increasingly used as endpoint for assessment of efficacy in some trials so to assign this category when no lesions can be measured is not advised.

## 6.1.5 Duration of Response

Duration of overall response: The duration of overall response is measured from the time measurement criteria are met for CR or PR (whichever is first recorded) until the first date that recurrent or progressive disease is objectively documented (taking as reference for progressive disease the smallest measurements recorded since the treatment started).

The duration of overall CR is measured from the time measurement criteria are first met for CR until the first date that recurrent disease is objectively documented.

Duration of stable disease: Stable disease is measured from the start of the treatment until the criteria for progression are met, taking as reference the smallest measurements recorded since the treatment started.

#### 6.1.6 Progression-Free Survival

Progression-free survival (PFS) is defined as the duration of time from study enrollment to time of progression.

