# 2.2 Secondary Objectives

- 2.2.1 To assess the safety and tolerability of concurrent durvalumab and radiotherapy compared to historical data from patients treated with standard of care chemoradiation;
- 2.2.2 To determine the overall survival (OS) defined as the time from study enrollment to death due to any cause;
- 2.2.3 To determine the distant metastases-free survival defined as the time from the study enrollment to any new distant lesion;
- 2.2.4 To determine the local and regional control defined as the time from the study enrollment to any local and regional lesion;

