### 2.4 Endpoints

- 2.4.1 Primary endpoint of 12-month progression-free survival (PFS) rate is based on an assessment by an investigators according to RECIST 1.1 criteria; PFS is defined as the time from the study enrollment to documented progressive disease or death due to any cause, whichever occurs first;
- 2.4.2 Secondary endpoint of safety and tolerability will be assessed by adverse event according to CTCAE V.5;
- 2.4.3 Secondary endpoint of overall survival is defined as the time from study enrollment to death due to any cause;
- 2.4.4 Secondary endpoint of distant metastases free survival is defined as the time from the study enrollment to any new distant lesion;
- 2.4.5 Secondary endpoint of local and regional control defined as the time from the study enrollment to any local and regional lesion;
- 2.4.6 Exploratory endpoint of biomarker and biomarker correlatives;
- 2.4.7 Exploratory endpoint of proportion of patients alive at 12 and 24 months.

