#### 7.1.3 Adverse Reactions

In patients with Stage III NSCLC in the PACIFIC study (IMFINZI n=475), the most common adverse reactions (≥20% of patients) were cough (40%), fatigue (34%), pneumonitis or radiation pneumonitis (34%), upper respiratory tract infections (26%), dyspnea (25%), and rash (23%). The most common Grade 3 or 4 adverse reaction (≥3%) was pneumonia (7%).

In patients with Stage III NSCLC in the PACIFIC study (IMFINZI n=475), discontinuation due to adverse reactions occurred in 15% of patients in the IMFINZI arm. Serious adverse reactions occurred in 29% of patients receiving IMFINZI. The most frequent serious adverse reactions (≥2% of patients) were pneumonitis or radiation pneumonitis (7%) and pneumonia (6%). Fatal pneumonitis or radiation pneumonitis and fatal pneumonia occurred in <2% of patients and were similar across arms.

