#### 10.0 STATISTICAL CONSIDERATIONS

#### 10.1 Study Design/Study Endpoints

- 10.1.1 Study design: The study is a single armed, phase II trial to evaluate concurrent Durvalumab and radiotherapy followed by consolidative Durvalumab for Stage III Non-Small Cell Lung Cancer (NSCLC).
- 10.1.2 Primary endpoint of 12-month progression-free survival (PFS) rate is based on an assessment by an investigators according to RECIST 1.1 criteria; PFS is defined as the time from the study enrollment to documented progressive disease or death due to any cause, whichever occurs first;
- 10.1.3 Secondary endpoint of safety and tolerability will be assessed by adverse event according to CTCAE V.5;
- 10.1.4 Secondary endpoint of overall survival is defined as the time from study enrollment to death due to any cause;
- 10.1.5 Secondary endpoint of distant metastases free survival is defined as the time from the study enrollment to any new distant lesion:

- 10.1.6 Secondary endpoint of local and regional control defined as the time from the study enrollment to any local and regional lesion:
- 10.1.7 Exploratory endpoint of biomarker and biomarker correlatives;
- 10.1.8 Exploratory endpoint of proportion of patients alive at 12 and 24 months.

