#### 10.2 Accrual

In the PACIFIC trial, patients who received consolidative durvalumab after chemoradiation had a 12-month PFS rate of 55%. PFS was measured starting after completion of chemoradiation, when anti-PDL1 treatment was started. This represents the assumed performance of the experimental arm in this study. We recognize that all patients who were randomized in the PACIFIC trial had tolerated and not progressed on chemoradiation, which represents some degree of selection bias. The possibility of early progression or treatment intolerance were taken into account when selecting the margins for the non-inferiority design of this study. A sample size of 47 achieves 80% power to detect a non-inferiority against an upper hazard ratio of 1.4 using a log-rank test at a 0.1 significance level when the actual hazard ratio is 1.0 and the standard of care group hazard rate is 0.5978 (which is equal to 1-year PFS rate of 55% using an exponential model). Three additional patients will be enrolled (total N=50) to account for 5% loss to follow-up. Patients will be accrued for a period of 3 years with 1-year follow-up.

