#### 10.3 Data Analyses

#### 10.3.1 Survival outcome

Progression-free survival and overall survival will be estimated using the Kaplan-Meier approach and the corresponding confidence intervals will be estimated using Greenwood's formula. Distant metastases-free survival, local and regional control will be estimated using the Kaplan-Meier approach.

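### Section 6.1.6 leaves death out of PFS and so contradicts the primary endpoint definition; the distant and local-regional endpoints also need a rule for death

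*Combined protocol and SAP*

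**What the plan says.** **PFS.** Section 2.4.1 reads "PFS is defined as the time from the study enrollment to documented progressive disease or death due to any cause, whichever occurs first", and section 10.1.2 repeats it. Section 6.1.6, in the measurement chapter, reads "Progression-free survival (PFS) is defined as the duration of time from study enrollment to time of progression". No section ranks one definition above the other. Section 10.3.1 names Kaplan-Meier with Greenwood intervals for PFS and gives no event or censoring rule. Section 10.2 sizes the trial for "a non-inferiority against an upper hazard ratio of 1.4 using a log-rank test at a 0.1 significance level", starting from a 12-month PFS of 55%.

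**Distant metastases-free survival (DMFS).** Section 2.2.3 reads "To determine the distant metastases-free survival defined as the time from the study enrollment to any new distant lesion". Sections 2.4.4 and 10.1.5 agree, the latter as "Secondary endpoint of distant metastases free survival is defined as the time from the study enrollment to any new distant lesion". Death is an event in none of the three.

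**Local and regional control.** It runs from enrollment to a local or regional lesion. Section 10.3.1 says "Distant metastases-free survival, local and regional control will be estimated using the Kaplan-Meier approach". Nothing is said about a patient who dies without such a lesion.

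**The concern.** Two current sections give different event sets for the primary endpoint, and the incomplete one sits in the chapter where an assessor or programmer would look for the measurement rule. Under 6.1.6 a patient who dies before documented progression has no event and would be censored. In a given data set, turning an event into a censored time can only raise the Kaplan-Meier curve or leave it unchanged, so the direction of the error is certain. In a single-arm non-inferiority comparison it works in favour of the regimen, and a treatment-related death before progression would not count against it. The trial is open label and investigators assess progression, so the event rule should not be left open to choice.

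DMFS has a milder fault. The name promises survival free of distant disease, but the definition counts only the distant lesion, so the estimate would read higher than its label implies. It also differs from the time to death or distant metastasis reported for PACIFIC in section 1.1, although the protocol does not commit to that comparison.

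For local-regional control, if deaths are censored, 1 minus Kaplan-Meier is a net quantity. It exceeds the proportion of patients who actually fail locally or regionally.

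**Working it through.** **1. The plan's own figures (section 10.2).** The reference hazard is λ = −ln(0.55) = 0.5978 per year. At the margin, 12-month PFS is exp(−1.4 × 0.5978) = 43.3%, so the design separates 55% from 43.3%, a gap of 11.7 points. With uniform accrual over 3 years and 1 further year of follow-up, the event probability at hazard ratio 1.0 is

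p = 1 − [exp(−λ) − exp(−4λ)] / (3λ) = 0.7443.

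A one-sample log-rank test at one-sided 0.1 with 80% power needs

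N = [1.2816 × √(1.4p) + 0.8416 × √p]² / (0.4p)² = 46.7, so 47.

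Allowing for 5% loss, 47 / 0.95 = 49.5, so 50. The stated size is reproduced. It rests on a hazard rate and not on the wording of 6.1.6, so correcting that section leaves it unchanged. Section 10.2 does not state sidedness; one-sided is the reading that gives 47.

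**2. Bias in 12-month PFS if 6.1.6 is applied.** Let f be the share of the PFS hazard that is death without progression. With constant, independent hazards, Kaplan-Meier with deaths censored estimates S^(1−f). The documents do not give f, so 5% to 20% is assumed. Of the 50 × 0.45 = 22.5 first-year events expected at 55%, that is about 1 to 5 deaths.

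| f | True 55% reads | True 43.3% reads | Apparent hazard ratio when the true one is 1.4 |
|---|---|---|---|
| 5% | 56.7% | 45.2% | 1.33 |
| 10% | 58.4% | 47.1% | 1.26 |
| 20% | 62.0% | 51.2% | 1.12 |

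For example, 0.55^0.9 = 0.584 and 1.4 × 0.9 = 1.26. At f = 20% the upward shift at the margin is 7.9 points, about two thirds of the 11.7-point gap.

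**3. Where f may lie.** Section 7.1.3 says of PACIFIC: "Fatal pneumonitis or radiation pneumonitis and fatal pneumonia occurred in <2% of patients". In 50 patients that is fewer than 1 death, or under 1/22.5 = 4.4% of the expected first-year events. This points to the low end. Other causes of death are not given.

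**4. False non-inferiority at a true hazard ratio of 1.4.** The one-sample log-rank test was simulated with N = 47, one-sided 0.1, the accrual pattern above, deaths censored and 40,000 runs. Each range covers two variance forms: E, and (O + E)/2, where O and E are the observed and expected events.

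- f = 0: 9% to 10%
- f = 5%: 15% to 17%
- f = 10%: 24% to 26%
- f = 20%: 48% to 51%

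A separate normal approximation on the log hazard ratio with N = 50 gives 17%, 26% and 51% for the last three.

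**5. DMFS (illustration).** Take an exponential curve with the 28.3-month median from section 1.1, which counts death. At 24 months, 0.5^(24/28.3) = 55.6%. Leaving deaths out at f = 5% to 20% gives 0.556^(1−f) = 57.2% to 62.5%. The median becomes 28.3/(1−f) = 29.8 to 35.4 months.

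**6. Local-regional failure at 24 months (illustration).** Assume a failure hazard h = 0.2 per year. Then 1 − KM = 1 − exp(−0.4) = 33.0%. Cumulative incidence is h/(h+d) × [1 − exp(−2(h+d))], where d is the hazard of death without local-regional failure.

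- d = 0.1: 30.1%
- d = −ln(0.663)/2 = 0.205, from the 24-month survival of 66.3% in section 1.1: 27.4%

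The gap is 3 to 6 points. Over h = 0.1 to 0.3 and d = 0.05 to 0.205 it is 1 to 7 points. The 95% half-width around 33% with 50 patients is 1.96 × √(0.33 × 0.67/50) = 13 points.

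**The case against.** The endpoint and statistics sections agree with each other and both include death. Section 6.1 reads as generic response-criteria text: it defines duration of response and of stable disease, which are not endpoints here. A sensible analyst would follow 2.4.1 and 10.1.2 and treat 6.1.6 as an incomplete sentence. This is the likeliest outcome, and it is why the point does not rank higher. It does not remove the defect, because both texts are current, neither is given precedence, and section 10.3.1 does not settle the matter.

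The large error rates depend on 6.1.6 being used and on an assumed share of deaths, and the one related figure falls below the lowest share shown. The log-rank test appears only in the sample-size paragraph, and the analysis section names no test or decision rule. The calculation also takes the 55% benchmark to count deaths, which section 10.2 does not say. All of this stands. The error rates show how sensitive the design is; they do not forecast the result.

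DMFS is defined the same way in all three places, so that fault lies in the label and is not a contradiction. The local-regional endpoint is descriptive and its hazards are assumed. The 0.205 is an all-cause death hazard that includes deaths after local-regional failure, so it overstates d. These limits keep both points secondary.

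**Conclusion.** The concern holds. The sentence in 6.1.6 is wrong as a definition of this trial's primary endpoint and should be corrected before analysis. If it were applied, 12-month PFS would read about 2 to 8 points too high for an assumed 5% to 20% share of deaths without progression, with the low end the more plausible on the protocol's own evidence. The direction needs no such assumption. The size rests on constant, independent hazards and on a benchmark that counts deaths. If 2.4.1 and 10.1.2 are followed, there is no bias in PFS.

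The two secondary points also hold, at lower weight. DMFS as defined would overstate survival free of distant metastasis. Censoring deaths in the local-regional analysis would overstate failure, and so understate control, by a few points. That is the opposite direction from the PFS error and is small beside the sampling error.

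**What to change.** **First:** replace the sentence in 6.1.6 with the definition in 2.4.1 and 10.1.2, so that the event is the earlier of documented progression and death from whatever cause. Alternatively, delete it and refer to 2.4.1.

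**Then, at lower priority:**

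- In 2.2.3, 2.4.4 and 10.1.5, either add death from any cause as a DMFS event, or rename the endpoint time to distant metastasis and treat death as a competing event.
- In 10.3.1, estimate local-regional failure by cumulative incidence, with death before such failure as a competing event.

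The PFS and DMFS changes are wording only, because deaths are already collected for overall survival. The local-regional change swaps the estimator and needs no new data if it is limited to first progression. The sample size does not change.

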#### 6.2 Safety/tolerability

Analyses will be performed for all subjects having received at least one dose of study therapy. The study will use the CTCAE version 5.0 for reporting of adverse events. https://ctep.cancer.gov/protocolDevelopment/electronic applications/ctc.htm

#### 7.0 ADVERSE EVENTS

#### 7.1 Experimental Therapy

For the most recent safety update (in drug studies), please refer to the current Investigator's Brochure or Study Agent Prescribing Information.

#### 7.1.1 Contraindications

There are no contraindications for IMFINZI® (durvalumab).

#### **7.1.2** Special Warnings and Precautions for Use

IMFINZI can cause serious, potentially fatal adverse reactions including immunemediated pneumonitis, hepatitis, colitis or diarrhea, endocrinopathies, nephritis, rash or dermatitis, other immune-mediated adverse reactions, infection, and infusion-related reactions.

#### 7.1.3 Adverse Reactions

In patients with Stage III NSCLC in the PACIFIC study (IMFINZI n=475), the most common adverse reactions (≥20% of patients) were cough (40%), fatigue (34%), pneumonitis or radiation pneumonitis (34%), upper respiratory tract infections (26%), dyspnea (25%), and rash (23%). The most common Grade 3 or 4 adverse reaction (≥3%) was pneumonia (7%).

In patients with Stage III NSCLC in the PACIFIC study (IMFINZI n=475), discontinuation due to adverse reactions occurred in 15% of patients in the IMFINZI arm. Serious adverse reactions occurred in 29% of patients receiving IMFINZI. The most frequent serious adverse reactions (≥2% of patients) were pneumonitis or radiation pneumonitis (7%) and pneumonia (6%). Fatal pneumonitis or radiation pneumonitis and fatal pneumonia occurred in <2% of patients and were similar across arms.

#### 7.2 Adverse Event Monitoring

Adverse event data collection and reporting, which are required as part of every clinical trial, are done to ensure the safety of subjects enrolled in the studies as well as those who will enroll in future studies. Adverse events are reported in a routine manner at scheduled times during a trial. Additionally, certain adverse events must be reported in an expedited manner to allow for optimal monitoring of subject safety and care.

All subjects experiencing an adverse event, regardless of its relationship to study therapy, will be monitored until:

- the adverse event resolves or the symptoms or signs that constitute the adverse event return to baseline or is stable in the opinion of the investigator;
- there is a satisfactory explanation other than the study therapy for the changes

observed; or ➤ death.

#### 7.2.1 Definitions

An adverse event is defined as any untoward or unfavorable medical occurrence in a human research study participant, including any abnormal sign (for example, abnormal physical exam, imaging finding or clinically significant laboratory finding), symptom, clinical event, or disease, temporarily associated with the subject's participation in the research, whether or not it is considered related to the subject's participation in the research.

Adverse events encompass clinical, physical and psychological harms. Adverse events occur most commonly in the context of biomedical research, although on occasion, they can occur in the context of social and behavioral research. Adverse events may be expected or unexpected.

#### Adverse event of special interest

An adverse event of special interest (AESI) is one of scientific and medical interest specific to understanding of the Investigational Product and may require close monitoring. An AESI may be serious or non-serious.

If the Investigator has any questions in regards to an event being an imAE, the Investigator should promptly contact the Study Physician.

AESIs observed with durvalumab include:

- Diarrhea / Colitis and intestinal perforation
- Pneumonitis / ILD
- hepatitis / transaminase increases
- Endocrinopathies (i.e. events of hypophysitis/hypopituitarism, adrenal insufficiency, hyper- and hypothyroidism and type I diabetes mellitus)
- Rash / Dermatitis
- Nephritis / Blood creatinine increases
- Pancreatitis / serum lipase and amylase increases
- Myocarditis
- Myositis / Polymyositis Neuropathy / neuromuscular toxicity (e.g. Guillain-Barré, and myasthenia gravis)
- Other inflammatory responses that are rare / less frequent with a
  potential immune-mediated aetiology include, but are not limited to,
  pericarditis, sarcoidosis, uveitis and other events involving the eyeskin,
  haematological and rheumatological events, vasculitis, non infectious
  meningitis and non-infectious encephalitis.

In addition, infusion-related reactions and hypersensitivity/anaphylactic reactions with a different underlying pharmacological aetiology are also considered AESIs.

Further information on these risks (e.g. presenting symptoms) can be found in the current version of the durvalumab Investigator's Brochure. More specific guidelines for their evaluation and treatment are described in detail in the Dosing Modification and Toxicity Management Guidelines (please see Appendix I). These guidelines have been prepared by the Sponsor to assist the Investigator in the exercise of his/her clinical judgment in

treating these types of toxicities. These guidelines apply to AEs considered causally related to the study drug/study regimen by the reporting investigator.

